#### 8.0 STATISTICAL ANALYSIS PLAN

# 8.1 Statistical Analysis Plan Summary

This section contains a brief summary of the statistical analyses for this trial. Full detail is in the Statistical Analysis Plan (SAP) (Section 8.2).

04T4BY

**Protocol/Amendment No.:** 002-01

# 8.1.1 Efficacy Analysis

The primary and key secondary endpoints, primary analysis population, and primary analysis method that will be employed for the efficacy analyses are presented in Table 9. To address the primary hypothesis that ertugliflozin is non-inferior to glimepiride in A1C reduction at Week 52, the change from baseline in A1C at Week 52 will be analyzed using a constrained longitudinal data analysis (cLDA) method proposed by Liang and Zeger [15]. The cLDA model will include terms for treatment, time, prior antihyperglycemic medication (monotherapy or dual therapy), baseline eGFR, and the interaction of time by treatment with the restriction of a common baseline mean across treatment groups. An unstructured covariance matrix will be used to model the correlation among repeated measurements. The comparisons of interest will be ertugliflozin 15 mg vs. glimepiride, and ertugliflozin 5 mg vs. glimepiride. The primary hypothesis regarding the non-inferiority of ertugliflozin 15 mg versus glimepiride in decreasing A1C will be assessed using the estimated treatment difference from the cLDA model. If the upper bound of the two-sided 95% confidence interval (CI) for the mean difference between ertugliflozin 15 mg and glimepiride is less than the non-inferiority margin,  $\delta = 0.3\%$ , then ertugliflozin 15 mg will be declared non-inferior to glimepiride in terms of A1C reduction at Week 52. The non-inferiority test for ertugliflozin 5 mg in A1C reduction will use the same approach described above for ertugliflozin 15 mg dose level under the multiplicity control strategy described in Section 8.1.3.

Analyses of the change from baseline in body weight and in systolic blood pressure at Week 52 will be performed using the cLDA model as described above.

The primary analysis time point will be Week 52.

Data obtained after the initiation of rescue therapy or after a subject undergoes bariatric surgery will be censored (i.e., treated as missing) in the analyses of efficacy endpoints to avoid the confounding influences of rescue therapy and bariatric surgery. The primary analysis population for all efficacy analyses will be the Full Analysis Set (FAS), comprised of all subjects who receive at least one dose of study therapy and have at least one measurement of the endpoint of interest (either at baseline or post-randomization).

Table 9 Summary of Analysis Strategy for Key Efficacy Endpoints

Endpoint/Variable (Description, Time Point)	Statistical Method	Analysis Population	Missing Data Approach
Primary			
A1C – Change from baseline at Week 52	cLDA	FAS	Model-based
Key Secondary			
Body weight – Change from baseline at	cLDA	FAS	Model-based
Week 52			
Systolic blood pressure – Change from	cLDA	FAS	Model-based
baseline at Week 52			

04T4BY

**Protocol/Amendment No.:** 002-01

# 8.1.2 Safety Analysis

The All-Subjects-as-Treated (ASaT) population will be used for safety analyses. Safety and tolerability will be assessed following a tiered-approach by clinical review of all relevant parameters including AEs, pre-defined limits of change (PDLCs; see Section 12.6), laboratory tests, vital signs, and ECG. Adverse events associated with urinary tract infection, male and female genital mycotic infection, hypovolemia and symptomatic hypoglycemia AE will be considered as prespecified safety parameters (Tier-1) for which p-values and 95% confidence intervals (CIs) for between-treatment differences will be provided using the Miettinen and Nurminen method [16]. The AE terms associated with these Tier 1 events will be identified prior to unblinding.

# 8.1.3 Multiplicity

The type I error rate will be controlled at  $\alpha$ =0.05 level (2 sided) for all efficacy hypotheses via a combination of ordered testing and the Hochberg procedure [17] as follows. This strategy is depicted in Figure 2.

- Ordered testing ( $\alpha$ =0.05) for the following 6 tests:
  - o A1C non-inferiority, ertugliflozin 15 mg vs. glimepiride
  - o Hypoglycemia superiority, ertugliflozin 15 mg vs. glimepiride
  - o Body weight superiority, ertugliflozin 15 mg vs. glimepiride
  - o A1C non-inferiority, ertugliflozin 5 mg vs. glimepiride
  - o Hypoglycemia superiority, ertugliflozin 5 mg vs. glimepiride
  - o Body weight superiority, ertugliflozin 5 mg vs. glimepiride
- If the success criterion is achieved for all of the above six tests, the Hochberg procedure ( $\alpha$ =0.05 or 0.025) will be used for the following two tests:
  - o Systolic blood pressure superiority, ertugliflozin 15 mg vs. glimepiride
  - o Systolic blood pressure superiority, ertugliflozin 5 mg vs. glimepiride
- If the success criterion is met for both of the above two tests for systolic blood pressure, then the following two tests will be conducted in order ( $\alpha$ =0.05):
  - o A1C superiority, ertugliflozin 15 mg vs. glimepiride
  - o A1C superiority, ertugliflozin 5 mg vs. glimepiride.

**Protocol/Amendment No.:** 002-01

# 8.1.4 Power and Sample Size

The trial will randomize approximately 1230 subjects in a 1:1:1 ratio among the 3 treatment groups. A sample size of 410 per arm will provide 97% power to declare non-inferiority in A1C reduction at Week 52 between a given ertugliflozin dose and glimepiride, using a non-inferiority margin of 0.3%, assuming the true mean difference in A1C is 0%, based on the primary analysis population (FAS). The half-width of the 95% CI is expected to be 0.15%. The probability of meeting the non-inferiority criterion for both ertugliflozin doses in the FAS is 95%. In the secondary analysis population (Per-protocol), the power for declaring non-inferiority is 92% per dose, and 85% for both doses. The above calculations are based on the variability and subject attrition assumptions specified in Section 8.2.6.

#### 8.2 Statistical Analysis Plan

This section outlines the statistical analysis strategy and procedures for the trial. If, after the trial has begun, but prior to any unblinding, changes are made to primary and/or key secondary objectives, or the statistical methods related to those objectives, then the protocol will be amended (consistent with ICH Guideline E-9). Changes to exploratory or other non-confirmatory analyses made after the protocol has been finalized, along with an explanation as to when and why they occurred, will be listed in the Clinical Study Report (CSR) for the trial. Post-hoc exploratory analyses will be clearly identified in the CSR. No separate Statistical Analysis Plan (SAP) will be issued for this trial.

The statistical analysis of the data obtained from this trial will be the responsibility of the designee of the Sponsor.

This trial will be conducted as a double-blind trial. After all subjects complete Phase A (Visit 9/Week 52), medical/scientific review has been performed based on Phase A data, protocol deviators based on Phase A have been identified, and Phase A data have been declared final and complete, the trial will be unblinded to the Sponsor or the designee of the Sponsor. A CSR will be generated to support regulatory filing. This report will address the study's primary hypotheses and, hence, is not considered an interim analysis.

After Visit 9/Week 52, investigators and subjects will remain blinded to study drug treatment assignment until all subjects have completed the trial. At the end of the trial (including the 14 days after the last dose of blinded investigational product), the official, final database will be frozen and unblinded after medical/scientific review has been performed, protocol deviators have been identified, and data have been declared final and complete. A separate study report will be prepared after all subjects complete the trial.

#### 8.2.1 Analysis Endpoints

Safety and efficacy endpoints that will be evaluated for within- and/or between-treatment differences are listed below.

The baseline value will be defined as the Visit 4/Week 0/Day 1 (Randomization) measurement. If this measurement is not available, the last pre-randomization measurement on or after Week -2 will be used as the baseline value. The primary time point of the trial is Week 52.

MK-8835-002-01 Final Protocol

Output

Protocol/Amendment No.: 002-01

The mapping of relative day ranges to Week is provided in Section 12.7.

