## **Guidance for Other Medications**

The investigator or subject's physician/health care provider is permitted to make adjustments in the subject's non-AHA therapies throughout the trial if clinically warranted. Guidance for specific medications which are permitted during the study is provided below.

- 1. Blood Pressure and Lipid-altering Medications: Concurrent blood pressure and lipid-lowering medications are permitted. Subjects should be on stable doses of these medications for at least 4 weeks before Visit 4/Randomization (Day 1) and during the study. Subjects whose blood pressure or lipid-lowering medications are not stable at Visit 1/Screening should be scheduled appropriately to ensure these medications are stable for at least 4 weeks prior to Visit 4/Randomization (Day 1).
- 2. Hormonal Replacement Therapy and Birth Control Medications: Hormone replacement therapy and birth control medications are permitted, but subjects should be on stable regimens, and are expected to remain on their stable regimen while receiving blinded investigational product during the double-blind treatment period and for 14 days after the last dose of blinded investigational product.
- 3. Thyroid Hormone Replacement Therapy: Thyroid replacement medication (e.g., thyroxine) is permitted, but subjects should be on a stable dose for at least 6 weeks prior to Visit 1/Screening. Subjects who meet the TSH exclusion criterion specified in Table 3 may be re-screened after being on a stable thyroid replacement regimen for at least 6 weeks.
- 4. Supplemental and/or Traditional Medicines: The use of herbal supplements and other natural products should be discouraged. Subjects who do not discontinue the use of such supplements prior to Visit 3/Week -2 or combined Visit 2/3 should be instructed not to change the use or dose of the supplement during the trial. Subjects should be instructed not to initiate new supplements during the trial.

04T4BY

Protocol/Amendment No.: 002-01

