# 6.0 TRIAL FLOW CHART

Trial Period :	Scre	ening	Run-In	Randomization				Doub	le-Blino	l Treatm	ent			
	Sere	5	Itun III	Tuntomization				]	Phase A	/Year 1				
Visit Number	1	2 a	3ª	4	TC b	5	$TC^b$	6	7	8	TCb	9	TCb	10
Scheduled Week			-2	0 (Day 1)	3	6	9	12	18	26	32	39	45	52
Visit Window Guideline (days)			+/-5	+/-5		+/-7		+/-7	+/-7	+/-7		+/-14		+/-14
Administrative Procedures	•		,								1			
Informed Consent f	X													
Informed Consent for Future Biomedical Research g	X													
Assignment of Screening Number	X													
Contact IVRS	X		X	X		X		X	X	X		X		X
Subject Identification Card		X												
Assignment of Randomization Number				X										
Trial Compliance														
Inclusion/Exclusion Criteria	X		X	X										
Prior/Concomitant Medication Review	X	X	X	X		X		X	X	X		X		X
Diet and Activity Counseling/ Monitoring h		X	X	X		X		X	X	X		X		X
Dispense Hypoglycemia Assessment Log (HAL) and Instruct on Hypoglycemia Symptoms and Management		X												
Dispense Glucose Meter and Provide SMBG Instruction		X												
Investigational Product/Rescue Mo	edication	L												

MK-8835-002-01 Final Protocol

Confidential

26-Feb-2015

Trial Period :	Como	ening	Run-In	Randomization				Doub	le-Blind	l Treatm	ent			
	Scre	ening	Kun-in	Kandomization				]	Phase A	/Year 1				
Visit Number	1	2ª	3ª	4	TCb	5	TCb	6	7	8	TCb	9	$TC^b$	10
Scheduled Week			-2	0 (Day 1)	3	6	9	12	18	26	32	39	45	52
Dispense Single-Blind Placebo Run-in			X											
Witness Dose of Blinded Investigational Product in Clinic i			X	X										
Dispense Double-Blind Investigational Product				X		X		X	X	X		X		X
Dispense Glycemic Rescue Medication as Appropriate						X		X	X	X		X		
Assess Compliance with Blinded Investigational Product				X		X		X	X	X		X		X
Clinical Procedures/Assessments														
Demographics & Medical History	X													
Height	X													
Weight in Duplicate	X	X	X	X		X		X	X	X		X		X
Vital Signs in Triplicate (Pulse Rate and Blood Pressure)	X	X	X	X		X		X	X	X		X		X
Postural (Orthostatic) Blood Pressure/Pulse Rate in Duplicate			X	X		X				X				X
Full Physical Exam			X											
Brief Physical Exam j										X				X
12-Lead ECG k			X	X										X
Site Fingerstick A1C Measurement 	X													
Fasting Fingerstick Glucose in Clinic				X		X		X	X	X		X		X
Review of SMBG Measurements and HAL			X	X	X	X	X	X	X	X	X	X	X	X

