		Phase	B/Year 2		Rescue	Post-1re	atment
Visit Number	11	12	13	14	Rescue c	Discontinuation	Follow-up
Scheduled Week	65	78	91	104		At time of Discontinuation d	14-Day Post Treatment Telephone Contact e
Clinic							
Review of SMBG Measurements and HAL	X	X	X	X	X	X	
Assess Subjects for Potential Rescue or Discontinuation from Blinded Investigational Product, Based on Central Laboratory FPG/A1C	X	X	X				
Adverse Event Monitoring	X	X	X	X	X	X	X
Laboratory Procedures/Assessmen	ts						
FPG	X	X	X	X	X	X	
A1C m	X	X	X	X	X	X	
Fasting C-peptide o					X	X	
Proinsulin o					X	X	
Lipid Panel p				X	X	X	
Chemistry Panel	X	X	X	X	X	X	
Hematology		X		X	X	X	
Urine Collection (Urinalysis and Urine Albumin/Creatinine Ratio) q		X		X	X	Х	
Urine Pregnancy Test (women of childbearing potential only) r	X	X	X	X	X	X	
Plasma and serum for Future Biomedical Research				X	X	X	

Trial Period :		Double-Blin	d Treatme	nt	Rescue	Post Treatment			
		Phase I	3/Year 2		Rescue	Post-Treatment			
Visit Number	11	12	13	14	Rescue c	Discontinuation	Follow-up		
Scheduled Week	65	78	91	104		At time of Discontinuation d	14-Day Post Treatment Telephone Contact e		

- a. Subjects on metformin ≥1500 mg/day for ≥8 weeks prior to Visit 1/Screening, with a Visit 1/Screening A1C ≥7.0% and ≤9.0% (≥53 mmol/mol and ≤75 mmol/mol) can directly enter a combined Visit 2/3. Subjects requiring adjustment of blood pressure or lipid-lowering medication and subjects who are not fasting at Visit 1 should NOT have a combined visit. All procedures performed at Visit 2 and Visit 3/Week -2 must be performed at the combined Visit 2/3.
- b. Site personnel will contact subjects to assess glycemic control and collect adverse events.
- c. Immediately prior to initiation of rescue medication (at a scheduled or unscheduled visit), subjects meeting rescue criteria must undergo the Rescue Visit procedures.
- d. Subjects who discontinue taking investigational product prematurely should complete procedures for the Discontinuation Visit. These subjects will also be contacted via telephone by the investigator/qualified designee according to the same schedule as if the subject were still taking investigational product to collect SAEs and events eligible for adjudication (see Section 5.8.1).

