# **8.2.3.1** Statistical Methods for Efficacy Analyses

# Phase A (Week 0 to Week 52)

The primary efficacy analyses will compare the efficacy of ertugliflozin relative to glimepiride in change from baseline in A1C at Week 52. The mean change from baseline in A1C at Week 52 in the ertugliflozin 15 mg group will be compared to that in the glimepiride group using the estimated treatment difference via a constrained longitudinal data analysis (cLDA) model, proposed by Liang and Zeger [15]. This cLDA model assumes a common mean across treatment groups at baseline and a different mean for each treatment at each of the post-baseline time points. In this model, the response vector consists of baseline values and the values observed at each post-baseline time point. The cLDA model will include terms for treatment, time, prior antihyperglycemic medication (monotherapy or dual therapy), baseline eGFR, and the interaction of time by treatment. Time will be treated as a categorical variable so that no restriction is imposed on the trajectory of the means over time. The treatment difference in terms of mean change from baseline to a given time point will be estimated and tested from this model. Ertugliflozin 15 mg will be declared non-inferior to glimepiride in terms of A1C reduction if the upper limit of the two-sided 95% confidence interval (CI) for the mean difference between ertugliflozin 15 mg and glimepiride at Week 52 is less than the non-inferiority margin,  $\delta$ =0.3%. This margin was chosen because changes from baseline smaller than -0.3% have limited clinical impact, and the 0.3% margin balances lesser clinical impact with a study sample size that is feasible to conduct. The non-inferiority test for ertugliflozin 5 mg in A1C reduction will use the same approach described above following the multiplicity control strategy in Section 8.2.5. If non-inferiority is declared for ertugliflozin 15 mg, then an assessment of superiority will be conducted following the multiplicity control strategy described in Section 8.2.5. For the cLDA model, the Kenward-Roger adjustment will be used with restricted (or residual) maximum likelihood (REML) to make proper statistical inference. An unstructured covariance matrix will be used to model the correlation among repeated measurements and hence avoids the potential bias that could result from the use of specific structured covariance models. If the unstructured covariance model fails to converge with the default Newton-Raphson algorithm, the Fisher scoring algorithm or other appropriate methods can be used to provide initial values of the covariance parameters. In the rare event that none of the above methods yield convergence, a structured covariance such as Toeplitz can be used to model the correlation among repeated measurements. In this case, the empirical option will be used because the sandwich variance estimator is asymptotically unbiased while the model-based variance estimator can substantially overestimate or underestimate the true variance. The cLDA model uses the maximum likelihood principle to estimate the parameters and account for missing data in an implicit fashion. Values of eGFR that are >120 mL/min/1.73 m^2 will be set to 120  $mL/min/1.73 m^2$ .

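### The confirmatory systolic BP model is valid but leaves out a second triplicate pre-randomization BP reading that is already scheduled for every subject; adding it gives a modest, unbiased gain in precision.

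*Combined protocol and SAP*

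**What the plan says.** Section 8.2.1 fixes the baseline: "The baseline value will be defined as the Visit 4/Week 0/Day 1 (Randomization) measurement". The next sentence gives earlier readings their only role: "If this measurement is not available, the last pre-randomization measurement on or after Week -2 will be used as the baseline value".

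Section 8.1.1 applies the A1C model to SBP: "Analyses of the change from baseline in body weight and in systolic blood pressure at Week 52 will be performed using the cLDA model". Section 8.2.3.1 describes that model's outcome data: "In this model, the response vector consists of baseline values and the values observed at each post-baseline time point". Besides treatment and time, the terms are "prior antihyperglycemic medication (monotherapy or dual therapy), baseline eGFR". No efficacy model uses a Week -2 value when the Visit 4 value is present.

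The Section 6.0 flow chart row "Vital Signs in Triplicate (Pulse Rate and Blood Pressure)" is marked at Visits 1, 2, 3 (Week -2) and 4. Footnote a covers subjects who skip the stabilization period: "All procedures performed at Visit 2 and Visit 3/Week -2 must be performed at the combined Visit 2/3". A Week -2 BP is therefore scheduled for everyone. On BP and lipid drugs, Section 5.5 says: "Subjects should be on stable doses of these medications for at least 4 weeks before Visit 4/Randomization (Day 1) and during the study".

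**The concern.** A single visit's BP, even in triplicate, is a noisy measure of a subject's usual level. A second reading about two weeks earlier, taken by the same procedure, would normally carry further information about Week 52 SBP. Because it precedes randomization, its expected value is the same in all arms by design, so using it cannot bias the comparison.

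The precision matters because SBP for both doses forms the Hochberg step of the confirmatory sequence (Sections 8.1.3 and 8.2.5). Superiority on A1C is tested only if both SBP tests succeed.

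**Working it through.** **1. Reproduce the plan's figure.** Table 15 gives an effective n of 337 per arm, SD 11.2 mm Hg and 90% power; the test is two-sided at 0.05.

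Detectable difference = (1.960 + 1.282) × 11.2 × √(2/337) = 2.797 mm Hg, against 2.8 stated. Power at 2.8 is 90.1%. The effective n, recomputed from the attrition rates and A1C correlation matrix in Section 8.2.6, is 337.4 against 337. The power section stands.

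**2. Effect of a second pre-randomization reading.** Let r be the correlation of each pre-randomization reading with Week 52, taken as equal for the two, and r12 the correlation between the readings. The documents give neither, so both are assumptions.

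- Residual variance with one reading: 1 − r²
- Residual variance with two readings: 1 − 2r²/(1 + r12)
- Variance ratio: the second divided by the first

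| r | r12 | Variance ratio | Reduction |
|---|---|---|---|
| 0.4 | 0.75 | 0.817/0.840 = 0.973 | 2.7% |
| 0.5 | 0.7 | 0.706/0.750 = 0.941 | 5.9% |
| 0.5 | 0.6 | 0.688/0.750 = 0.917 | 8.3% |
| 0.5 | 0.5 | 0.667/0.750 = 0.889 | 11.1% |
| 0.6 | 0.5 | 0.520/0.640 = 0.8125 | 18.8% |

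The first and last rows are the extremes of the assumed ranges (r 0.4–0.6, r12 0.5–0.75). The last is a generous corner, because it has visits two weeks apart correlating less than visits a year apart.

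**3. Unequal correlations.** Let Week -2 correlate with Week 52 at 0.05 less than Visit 4 does. With correlations a and b, the explained share is (a² + b² − 2ab·r12)/(1 − r12²).

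| Visit 4 with Week 52 | Week -2 with Week 52 | r12 | Variance ratio |
|---|---|---|---|
| 0.5 | 0.45 | 0.6 | 0.953 |
| 0.5 | 0.45 | 0.7 | 0.974 |
| 0.6 | 0.55 | 0.7 | 0.948 |
| 0.4 | 0.35 | 0.6 | 0.977 |

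The gain is then about 2–5%.

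**4. Missing data.** The full cLDA information was computed with the Section 8.2.6 attrition rates and assumed SBP correlations that were either constant (0.4–0.6) or slowly decaying. The variance ratios were 0.883–0.938, a 6–12% reduction. Attrition does not remove the gain.

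**5. In mm Hg.** This step treats 11.2 as a baseline-adjusted SD. At r = 0.5:

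- r12 = 0.7: 2.797 × √0.941 = 2.71 mm Hg; power at 2.8 is 91.7%; equivalent n is 337/0.941 = 358
- r12 = 0.5: 2.797 × √0.889 = 2.64 mm Hg; power at 2.8 is 93.1%; equivalent n is 337/0.889 = 379

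**6. Both doses.** Under Hochberg, both SBP hypotheses are rejected when both p-values are below 0.05. The shared glimepiride arm gives the two test statistics a correlation of 0.5. With a true difference of 2.8 mm Hg for each dose and the same SD assumption, the probability that both succeed is about 83% now and 86–88% with the extra reading (r = 0.5, r12 0.7 to 0.5). The plan does not state this joint power for SBP.

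**The case against.** The strongest case against is that nothing here is broken. Taking the randomization visit as baseline is ordinary practice, that reading is already a triplicate, Week -2 data do have a fallback role, and Table 15 reaches its stated 90%. All of that stands. A reader might infer that the SBP analysis is biased or underpowered; the documents support neither.

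Four further points limit the size and reach of the gain.

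- **Size.** A reader might expect a gain of at least 5% of variance. The assumed ranges do not guarantee that: the low corner gives 2.7%, at which the detectable difference is 2.76 mm Hg and still rounds to 2.8. Slightly unequal correlations also pull the gain to 2–5%.
- **SD.** Section 8.2.6 calls the A1C SD conditional, but Table 15 puts no such label on the 11.2 mm Hg, which comes from a study of another SGLT2 inhibitor. The mm Hg and power figures depend on that reading; the percentage reductions do not.
- **Regimen.** It is tempting to say that every Week -2 reading is on the same stable regimen. The note to exclusion 35 lets Visit 4 be rescheduled when BP medication has not been stable for 4 weeks, so some Visit 3 readings may precede a change and be more than two weeks old. This weakens the correlation in those subjects but introduces no bias.
- **Consequence.** SBP is tested only after six earlier successes. The A1C superiority tests behind it are not powered, since the sample size assumes a true A1C difference of 0%. Diastolic BP and FPG lie outside the confirmatory sequence, and no gain was calculated for them.

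These points set the weight of the recommendation. None of them argues against using a valid reading that is already being collected.

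**Conclusion.** The point holds as a low-cost efficiency improvement. The current SBP analysis is valid. It omits a pre-randomization reading that is scheduled for all subjects and can be used without bias.

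Under equal correlations with Week 52 of 0.4–0.6 and a between-visit correlation of 0.5–0.75, the variance of the treatment difference falls by about 3–19%, or 6–11% at r = 0.5 with r12 0.5–0.7. It falls by only about 2–5% if Week -2 is slightly less predictive than Visit 4. If 11.2 mm Hg is a baseline-adjusted SD, the detectable difference at r = 0.5 moves from 2.80 to about 2.64–2.71 mm Hg. All of these sizes rest on correlations that the documents do not supply. The confirmatory benefit arises only if the six earlier tests succeed.

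**What to change.** In Section 8.2.3.1, for SBP:

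- Add the value taken at Visit 3 or combined Visit 2/3 to the cLDA response vector as a separate pre-randomization time point. Give it its own mean, constrained equal across arms. The separate mean absorbs any run-in shift and the selection on BP at Visit 4 (exclusion 36).
- Add the same value as a covariate in the SBP ANCOVAs.
- Keep Visit 4 as the reported baseline and the reference for change.
- Name the visit explicitly. In Section 12.7 a Visit 3 value before Day 1 satisfies both the Week -2 and the Week 0 rule, and that overlap must be resolved.

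The same change may optionally be made for diastolic BP and for FPG, which is also drawn at Visit 3; both are supportive.

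The cost is one extra time level in the model, one extra ANCOVA covariate, and a departure from using one uniform model for all continuous endpoints. SBP is a key secondary endpoint, so Section 8.2 requires a protocol amendment before any unblinding; a wording change to the analysis section alone is not enough. No new data are needed.
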